## 7.1.2. Physical Examinations

Physical examinations may be conducted by a physician or another medically-qualified individual such as a physician's assistant or a nurse practitioner. A full physical examination will include head, ears, eyes, nose, mouth, skin, heart, lung, lymph nodes, and the gastrointestinal, musculoskeletal, and neurological systems. The targeted physical examination will be focused on general appearance, the respiratory and cardiovascular systems, and subject-reported symptoms.

# 7.1.3. Height and Weight Measurements

Height will be recorded during Screening.

For measuring weight, a scale with appropriate range and resolution should be used and must be placed on a stable, flat surface. Subjects must remove shoes, bulky layers of clothing, and jackets so that only light clothing remains. They must also remove the contents of their pockets and should remain still during measurement of weight.

## 7.1.4. Vital Signs

Temperature, blood pressure (BP), and pulse rate (PR) will be measured at times specified in the Schedule of Activities and Study Procedures section of this protocol.

Temperature should be measured orally.

Seated BP should be measured with the subject's feet flat on the floor and back supported and the subject's arm supported at the level of the heart. BP should be recorded to the nearest mm Hg after at least 5 minutes of rest. Subjects should be instructed not to speak during measurements. A properly sized and calibrated BP cuff should be used for each measurement. PR will be measured in the brachial/radial artery for at least 30 seconds. The use of an automated device for measuring BP and PR is acceptable. When the timing of these measurements coincides with a blood collection, BP and PR should be obtained prior to the nominal time of the blood collection with the exception of Screening and Pre-Dose.

On Day 1, vital signs will be measured pre-dose and at 15 minutes, 30 minutes, 60 minutes, 90 minutes, 2 hours, and 4 hours after dosing for all subjects (+/- 5 minutes). For subjects in the multiple dose cohorts, vital signs will be measured pre-dose and 30 minutes post-dosing (+/- 5 minute window) on Day 8, Day 15, and Day 22.

#### 7.1.5. Electrocardiograms

12-Lead ECGs should be obtained at times specified in the Schedule of Activities and Study Procedures section of this protocol.

All ECGs should be performed after the subject has rested quietly for at least 10 minutes in a supine position. The Principle Investigator or a medically qualified designee should review all ECG measurements obtained during the study. All ECG results should be reviewed for any clinically significant findings and consultation with a cardiologist should be obtained if necessary. Post-treatment ECG results should be compared to the Day 1 baseline ECG measurements.

The QT interval will be corrected to QTC-F (Fridericia); QTCF will be recorded in the eCRF.

QTc-F can be corrected with the following equation:

$$QTcF = \frac{QT}{\sqrt[3]{RR}}$$

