#### 6.2.4. Day 29 (Visit 5)

The following procedures will be completed on Day 29, which is the 'End of Study' Visit:

• Record any concomitant medications used by the subject since Day 8

- Assess adverse events by spontaneous reporting and by asking the subject to respond to a non-leading question such as "How do you feel?"
- Remind the subject about study contraception requirements and confirm highly effective contraception was used for 7 days after the last IP administration (if applicable)

The Day 29 visit may be conducted via telephone. However, the PI may also ask the subject to return to the site on Day 29 and conduct any additional evaluations or assessments required to protect the well-being of the subject.

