#### 6.3.3. Day 8 (Visit 4)

The following procedures will be completed on Day 8:

- Collect blood and urine samples for safety laboratory tests
- Collect pre-dose blood sample for PK analysis
- Collect pre-dose serum sample for PIIANP assessment
- Collect pre-dose urine sample for CTX-II assessment
- Collect pre-dose serum sample for biospecimen banking (if the subject has consented to provide this optional sample)
- Administer the WOMAC
- Record any changes in concomitant medications

- Conduct targeted physical examination
- Obtain weight
- Obtain pre-dose temperature and seated BP and PR
- Obtain 12-lead ECG
- Collect pre-dose synovial fluid sample for biospecimen banking (if the subject has consented to provide this optional sample)
- Administer KA34 or placebo
- Obtain temperature and seated BP and PR 30 minutes after dosing (+/- 5 minute window)
- Assess adverse events by spontaneous reporting and by asking the subject to respond to a non-leading question such as "How do you feel?"
- Remind the subject about study contraception requirements and confirm highly effective contraception is being used (if applicable)

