# 6.4. Subject Withdrawal

Subjects may withdraw from the study at any time at their own request or they may be withdrawn at any time at the discretion of the investigator or the Sponsor for safety reasons or due to the inability to comply with the protocol-required schedule of visits or procedures. Subjects who request to discontinue receipt of study treatment will be discontinued from the study. An early termination visit should be conducted for subjects who receive study drug and then are prematurely withdrawn from the study if at all possible.

The early termination visit will include a physical exam and documentation of weight, vital signs, ECG, and WOMAC score. A review of ongoing AEs, concomitant medications and confirmation of barrier or contraception use for male subjects at least 7 days from the last day of the received dose will be documented. Blood and urine will be collected for safety laboratory tests (hematology, chemistry, and urinalysis), PK, PIIANP, and CTXII analyses.

If a subject decides to withdraw consent, this should be explained in the source documentation. If possible, the investigator should inquire about the reason for withdrawal, request that the subject return for an early termination visit, and follow up with the subject regarding any unresolved AEs for 30 days.

If a subject does not return for a scheduled visit, every effort should be made to contact the subject. The investigator or site staff should attempt to contact the subject at least twice. After 2 attempts, site staff may send a registered letter to the subject. If no response is received, the subject will be considered lost to follow-up. All attempts to contact the subject

and information received during contact attempts must be recorded in the source documentation.

If the subject withdraws from the study and also withdraws consent for disclosure of future information, no further evaluations should be performed and no additional data should be collected. The Sponsor may retain and continue to use any data collected before such withdrawal of consent.

Subjects who are discontinued from or withdraw from the study may be replaced.

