6.4. Reference Start Date and Study Day

Study Day will be calculated from the reference start date, and will be used to show start/stop day of assessments and events.

Reference start date is defined as the day of the first dose of study medication, (Day 1 is the day of the first dose of study medication), and will appear in every listing where an assessment date or event date appears.

• If the date of the event is on or after the reference date then: Study Day = (date of event – reference date) + 1.

Document: CALIBR_CBR-KA34-3001_SAP_Final 1.0
Author: PPD Version Number: Final 1.0
Version Date: 15MAY2020

Template No: CE Reference: CE

Copyright © 2017 IQVIA. All Rights Reserved.

• If the date of the event is prior to the reference date then: Study Day = (date of event – reference date).

In the situation where the event date is partial or missing, Study Day, and any corresponding durations will appear partial or missing in the listings.

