6.6. RETESTS, UNSCHEDULED VISITS AND EARLY TERMINATION DATA

Unscheduled measurements will not be included in summary statistics, but will contribute to the assessment of clinical outliers. Early termination results will be recorded as such, and included with the end-of-study summaries.

In the case of a retest of a scheduled assessment, the earliest available measurement for that scheduled time (i.e. the original assessment) will be used for summaries unless flagged as invalid.

Listings will include all scheduled, unscheduled, retest and early discontinuation data.

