17.4. ECG EVALUATIONS

Results of the ECG assessments will be included in the reporting of this study.

Overall interpretation of ECG will be summarized for the following categories:

- 0 Normal
- Abnormal, Not Clinically Significant (ANCS) 0
- Abnormal, Clinically Significant (ACS)

Number and percent of subjects for each category will be presented by dose levels and schedule assessment visit/day.

The following summary will be provided for 12-lead ECG parameters PQ interval (PR), RR interval (RR), QRS interval (QRS), QT interval (QT), QTc interval (QTcF) and Heart Rate (HR) based on the Safety Population.

Actual and change from baseline by dose levels and scheduled assessment visit/day for SAD and MAD study part

All ECG assessments will be listed for each study part.

Document: CALIBR CBR-KA34-3001 SAP Final 1.0

Author: PPD Version Number: Version Date:

Final 1.0 15MAY2020

Template No: CC Effective Date: 01Apr2016 Reference:

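### Do the ECG tables fall short because no ECG is scheduled in the hours after an injection and two kinds of ECG have no stated time from it?

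*Protocol*

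**What the plan says.** Protocol 7.1.5 leaves ECG times to the Schedule of Activities and Section 6, and sets the comparison: "Post-treatment ECG results should be compared to the Day 1 baseline ECG measurements". In both parts the Day 1 ECG precedes the injection. The later Day 1 measurements, from 15 minutes to 4 hours, are vital signs and PK samples, with an optional banked serum sample at 4 hours. After treatment starts, SAD subjects have one ECG (Day 8) and MAD subjects have four (Days 8, 29, 90 and 180). MAD Days 15 and 22 have injections but no ECG.

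MAD Day 8 is itself an injection day. Section 6.3.3 labels the vital signs just above the ECG, "Obtain pre-dose temperature and seated BP and PR", but gives the ECG no such label.

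For withdrawals, Protocol 6.4 says "The early termination visit will include a physical exam and documentation of weight, vital signs, ECG, and WOMAC score", with no interval from the last injection. SAP 6.6 then says "Early termination results will be recorded as such, and included with the end-of-study summaries". In SAD the end-of-study visit is Day 29 ("The following procedures will be completed on Day 29, which is the 'End of Study' Visit"), and its list has no ECG.

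SAP 17.4 specifies the ECG table as "Actual and change from baseline by dose levels and scheduled assessment visit/day for SAD and MAD study part" and lists every ECG. On unscheduled ECGs, SAP 6.6 says "Unscheduled measurements will not be included in summary statistics, but will contribute to the assessment of clinical outliers". Study Day is counted from the first dose: "Reference start date is defined as the day of the first dose of study medication".

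**The concern.** ECG change from baseline is a secondary endpoint, and ECG results are part of the safety review before each escalation (Protocol 3.2). If every clearly timed ECG falls long after the drug is expected to have left plasma, a clean table could be mistaken for reassurance about short-lived conduction or repolarisation effects.

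Two details seem to make this worse. At the MAD escalation review, Day 8 is the only post-treatment ECG that every subject is scheduled to have had. It describes either about a week after dose 1 or a short time after dose 2, and Study Day is the same in both cases. An early-termination ECG could also come from the dosing weeks, because subjects who ask to stop treatment leave the study. Pooled as SAP 6.6 says, it would sit beside MAD Day 180 values taken months after the last injection.

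**Working it through.** The plan gives no ECG sample-size or precision figure to reproduce, so the check is a count of ECGs against injections, followed by a reading of the two unlabelled cases.

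**Inputs.** Cohort sizes from Protocol 3.1: SAD 4 + 4 + 8 + 8 = 24; MAD 3 × 12 = 36; total 60, matching the stated figure. ECG visits from Protocol 6.2 and 6.3. Visit windows and the 7-day minimum between injections from the MAD schedule. A ±1 day window at SAD Day 8 is assumed.

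**1. Count of planned post-treatment ECGs**
- Total: 24 × 1 + 36 × 4 = 168.
- Nominally seven or more days after the latest injection: 24 + 36 × 3 = 132; 132/168 = 79%.
- Not labelled relative to that day's injection (MAD Day 8): 36/168 = 21%, of which 27 are active and 9 placebo.
- Fixed in the hours after an injection: 0.

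**2. Gap from the latest injection, in days.** With ±1 day windows and at least 7 days between injections, the fourth injection falls on Day 22 or 23.

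| ECG | Shortest | Longest |
|---|---|---|
| SAD Day 8 | 7 − 1 = 6 | 9 − 1 = 8 |
| MAD Day 29 | 28 − 23 = 5 | 30 − 22 = 8 |
| MAD Day 90 | 83 − 23 = 60 | 97 − 22 = 75 |
| MAD Day 180 | 150 − 23 = 127 | 210 − 22 = 188 |

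The shortest, 5 days, is 5 × 24 = 120 hours, or 120/4 = 30 times the 4 hours after which SAP 15.1 expects no quantifiable parent drug. The first part of the concern is therefore correct as fact.

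**3. MAD Day 8.** In 6.3.3 the ECG stands between the vital signs and the synovial fluid sample, both labelled pre-dose, and all three come before the injection. Elsewhere, unlabelled items in that position are pre-dose. The Day 1 ECG line in 6.3.1 has no label either, and the MAD schedule puts it in the pre-dose column. The first vital signs on Days 15 and 22 have no label, and 7.1.4 and schedule footnote B confirm that they are pre-dose. Day 8 vital signs need a label because they are taken twice; the ECG is taken once. Read this way, the Day 8 ECG falls 8 − 1 = 7 to 9 − 1 = 8 days after dose 1.

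**4. Early termination.** SAP 17.4 lists all ECGs, SAP 6.4 attaches Study Day and the first-dose date to listings, and SAP 14 lists study drug administration. Then

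days since last injection = Study Day of ECG − Study Day of last injection.

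For illustration, an ECG on Study Day 22 after a last injection on Study Day 15 gives 7 days. This assumes that the administration listing shows dates.

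**5. Size of the pooling effect.** One early-termination ECG among the 9 active subjects of a MAD dose level is 1/9 = 11%, or 1/10 = 10% if the subject is replaced. The other values are nominally 180 − 22 = 158 days after the last injection. The documents give no withdrawal rate; an assumed 0–20% gives 0 to 0.20 × 9 = 1.8 such ECGs per active dose level. SAP 6.1 shows a group with fewer than two values as not applicable, so a separate row would often be blank. In SAD the end-of-study visit has no scheduled ECG, so an end-of-study row would already hold early-termination values only.

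**The case for a change.** The best case for a change is that it would cost little: a sentence of limitation, a listing column, a table row and a label. The contrast with neighbouring sections is also real. The PK and PD sections require collection times in the CRF and 7.1.5 does not. SAP 17.5 tabulates vital signs by timepoint and SAP 17.4 does not do so for ECGs. List order is not strictly binding either: the WOMAC must come first at a visit, yet 6.3.3 places it after five sample collections.

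Part of this stands. Post-dose pulse and blood pressure say nothing about QTcF, PR or QRS, and unscheduled ECGs stay out of the summary tables. Whoever writes the report should not read acute cardiac safety into these tables. A pre- or post-dose label on the Day 8 ECG would be tidier.

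The rest is weaker. The WOMAC example shows loose order within the pre-dose block, not an item crossing the injection. The changes to the SAP would not reach the escalation decision, because SAP 4.1 places reporting to the safety board outside its scope. The label would need a protocol amendment with IRB/EC approval (Protocol 12.1), only to confirm what the list order already indicates. A written disclaimer would withdraw a conclusion that neither document draws. The table shells, which set the final layout, are not in these documents and may already show clock times or mark early-termination values.

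**Conclusion.** No change to the plan follows. None of the 168 planned post-treatment ECGs is fixed in the hours after an injection, so the tables describe changes about a week or more after dosing and are silent on acute interval effects. That is a fair trade-off for this trial. No acute-QT objective is stated and no formal safety tests are planned. Protocol 1.2.1 reports animal exposure margins of 240-fold or more. The telemetered dog study it describes found a small, transient blood-pressure fall at much higher exposure, and post-dose vital signs are scheduled with that in view.

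The two timing gaps are small and ones that analysts can fill. The 36 MAD Day 8 ECGs read as pre-dose from their place in the visit list; stating this explicitly would be an optional clarification, with the choice left to the sponsor's clinical team. Early-termination ECGs can be dated from the listings, and marking them within the end-of-study row would be a presentational refinement that alters no conclusion.

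This rests on three assumptions: sites follow the visit list in placing the Day 8 ECG before the injection, the administration listing carries dates, and withdrawal is not far above the assumed 0–20%.

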#### 2.4. Secondary Endpoints

- Changes from baseline in clinical laboratory test results, vital signs, or electrocardiogram (ECG) results
- Clinically significant findings on physical examination
- Pharmacokinetic parameters of KA34 in plasma including:
  - Maximum observed plasma concentration (Cmax)
  - Dose-adjusted Cmax (Cmax/dose)
  - Time to maximum observed plasma concentration (Tmax)
  - Area under the plasma concentration vs. time curve from time zero to the last quantifiable concentration (AUC $_{0-t}$ )
  - Dose-adjusted AUC0-t (AUC0-t/dose)

- AUC from time zero to infinity (AUC0-∞)
- Dose-adjusted AUC0-∞ (AUC0-∞/dose)
- Terminal elimination rate constant  $(\lambda_z)$
- Terminal half-life (t½)
- Apparent clearance (CL/F)
- Volume of distribution (Vz/F)

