# 9.5. Safety Analyses

Safety and tolerability will be evaluated by compiling standard summary statistics for treatment emergent adverse events (TEAEs), serious adverse events (SAEs), clinical laboratory test results, vital sign measurements, and electrocardiogram (ECG) findings. No formal statistical tests will be conducted on the safety or tolerability of KA34.

Changes from baseline for the ECG parameters including QT interval, heart rate, QTc interval, PR interval, and QRS interval will be summarized by treatment and time.

AEs, ECGs, BP, PR, and clinical laboratory data will be reviewed and summarized on an ongoing basis during the study to evaluate the safety of subjects. Safety data will be presented in tabular and/or graphical format and summarized descriptively, as appropriate.

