17.3. LABORATORY EVALUATIONS

Laboratory results will be included in the reporting of this study for Hematology, Blood Chemistry and Urinalysis. A list of laboratory assessments to be included in the outputs is included in the protocol, Section 7.1.1. Presentations will use SI Units, as provided by the labs.

Protocol-specified clinical laboratory tests will be summarized using descriptive statistics for the SAD and MAD parts. Clinical laboratory data collected during study conduct, which were not required per protocol, such as for special testing to evaluate an AE, will be listed separately and not summarized.

Quantitative laboratory measurements reported as "< X", i.e. below the lower limit of quantification (BLQ), or "> X", i.e. above the upper limit of quantification (ULQ), will be converted to X for the purpose of quantitative summaries, but will be presented as recorded, i.e. as "< X" or "> X" in the listings.

The following summaries will be provided for laboratory data:

 Actual, change from baseline and percentage change from baseline by dose levels and visit (for quantitative measurements)

Document: CALIBR_CBR-KA34-3001_SAP_Final 1.0
Author: PPD Version Number: Final 1.0
Version Date: 15MAY2020

Template No: Fefective Date: 01Apr2016

Copyright © 2017 IQVIA. All Rights Reserved.

- Shift from baseline according to normal range criteria (for quantitative measurements and categorical measurements) for all on-treatment assessments.
- Listing of lab results outside the normal range

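### SAP 17.4 summarises the overall ECG interpretation only as counts per visit, so new abnormalities (both parts) and subjects ever affected (multiple-dose part) are not tabulated by dose

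*Protocol*

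**What the plan says.** The endpoint. Protocol 2.4 lists as a secondary endpoint "Changes from baseline in clinical laboratory test results, vital signs, or electrocardiogram (ECG) results". Laboratory and ECG results stand in the same bullet.

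The review instruction. Protocol 7.1.5, in the paragraph on who reads the ECGs and when to consult a cardiologist, says "Post-treatment ECG results should be compared to the Day 1 baseline ECG measurements".

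The planned ECG outputs. SAP 17.4 has three:
- For the three-level overall interpretation: "Number and percent of subjects for each category will be presented by dose levels and schedule assessment visit/day".
- For PR, RR, QRS, QT, QTcF and heart rate: "Actual and change from baseline by dose levels and scheduled assessment visit/day for SAD and MAD study part". This covers the parameters that Protocol 9.5 names for change from baseline.
- "All ECG assessments will be listed for each study part".

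The comparison with laboratory data. SAP 17.3 plans, besides summaries of values and changes, "Shift from baseline according to normal range criteria (for quantitative measurements and categorical measurements) for all on-treatment assessments". SAP 17.4 names no such display for the ECG interpretation.

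The ECG schedule. After first dosing, the single-dose part has one scheduled ECG, on Day 8 (Protocol 6.2.3). The multiple-dose part has four, on Days 8, 29, 90 and 180 (Protocol 6.3.3, 6.3.6, 6.3.8 and 6.3.9).

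**The concern.** Counts made separately at each visit are marginal totals. They lose two things that matter for a safety reading by dose.

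First, they do not show whether a subject who is abnormal after dosing was already abnormal before it. Subjects are 40 to 75 years old and no eligibility criterion is specific to the ECG (exclusion 4 concerns laboratory abnormalities), so some abnormal tracings at baseline are to be expected. An unchanged count may mean that nothing happened, or that some subjects resolved while others became abnormal.

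Second, where there are several post-dose visits, the counts do not show whether the same or different subjects are abnormal at each.

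Mean changes in intervals do not fill the gap. Rhythm and morphology findings can leave the intervals unchanged and appear only in the interpretation. At stake is the categorical part of a stated secondary safety endpoint in a first-in-human trial.

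**Working it through.** The plan gives no ECG abnormality rate and no figure on this point, so there is nothing to reproduce. The check is to ask what the planned table can and cannot determine. All abnormal counts below are assumed for illustration. The group sizes and visit numbers come from the documents.

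**Inputs**
- Active subjects per multiple-dose cohort: 9 (Protocol 3.1).
- Active subjects per single-dose cohort: 3, 3, 6 and 6 (Protocol 3.1).
- Scheduled post-dose ECGs: 4 in the multiple-dose part, 1 in the single-dose part.

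**Step 1: subjects ever abnormal after dosing.** With n subjects and visit counts c1, c2, and so on, the number ever affected lies between max(c) and min(n, sum of c). For n = 9 and four visits:

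| Abnormal at each visit | Lowest number ever affected | Highest number ever affected |
|---|---|---|
| 1 | 1 of 9 (11%) | min(9, 4) = 4 of 9 (44%) |
| 2 | 2 of 9 (22%) | min(9, 8) = 8 of 9 (89%) |
| 3 | 3 of 9 (33%) | min(9, 12) = 9 of 9 (100%) |

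The low end is the same subjects abnormal throughout. The high end is as many different subjects as the counts allow.

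**Step 2: the same question in the single-dose part.** With one visit, max(c) and sum of c coincide. One abnormal of 6 on Day 8 means exactly 1 of 6. There is no ambiguity about the number abnormal at the scheduled post-dose ECG. This covers 4 + 4 + 8 + 8 = 24 of the 60 planned subjects.

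**Step 3: newly abnormal subjects at one visit.** With b abnormal at baseline and f abnormal at the visit, the number newly abnormal lies between max(0, f − b) and min(f, n − b).
- n = 9, b = 3, f = 3: from max(0, 0) = 0 to min(3, 6) = 3.
- n = 9, b = 2, f = 3: from max(0, 1) = 1 to min(3, 7) = 3.
- n = 6 (single-dose), b = 2, f = 2: from max(0, 0) = 0 to min(2, 4) = 2.

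This ambiguity is present in both parts.

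**Step 4: where else the information could be found.** All ECGs are listed, so exact counts can be recovered by hand. Abnormal findings that meet Protocol 8.2.2 become adverse events, and SAP 17.1 tabulates those per subject by dose. That route is conditional: a move from normal to abnormal without clinical significance need not meet any of the 8.2.2 conditions.

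**The case against.** The strongest reply is that the plan does what the protocol asks. Protocol 7.1.5 describes how the site reviews tracings and prescribes no table. The protocol's ECG analysis is in 9.5, which names intervals and heart rate, and SAP 17.4 gives change from baseline for all of them. A reader might infer that the SAP contradicts the protocol or drops the baseline comparison for ECGs. The documents do not support either reading.

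A reader might also infer that subjects affected cannot be counted in any cohort. That is wrong for the single-dose part, as step 2 shows. Early termination or unscheduled ECGs are the only exceptions there.

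A fourfold understatement is likewise tempting. Four is only the upper end of an assumed 1-to-4 range; one persistently abnormal subject gives the same table with no distortion.

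Nor does the gap show that the 50% pause rule in Protocol 3.2 would fail. The DSMB works from blinded reports that SAP 4.1 places outside its scope.

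Further points have weight. The listings hold the full information and groups are small. Clinically significant findings are the ones most likely to reach the adverse event tables. Vital signs have no shift table either. Safety analysis is descriptive, and a shift table for 3 to 9 subjects will be mostly empty. The table shells mentioned in SAP section 8 are not among the documents available and might already contain such a layout.

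These arguments narrow the point but do not remove it. A hand count from listings after unblinding is not a prespecified summary, and the SAP gives no reason for linking laboratory categories to baseline but not ECG categories from the same endpoint.

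**Conclusion.** The point holds in a limited form. As written, SAP 17.4 offers no baseline shift and no any-time-post-dose count for the ECG interpretation. New abnormalities in both parts, and subjects ever affected in the multiple-dose part (36 of the 60 planned subjects), are not tabulated by dose.

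The missing item is a table, not data, and the numeric ECG analysis is unaffected. The bounds in the working are exact for the counts shown, but those counts are assumed. The actual loss depends on how many subjects are abnormal at baseline and whether later abnormalities persist in the same subjects, which the documents do not say. The conclusion also assumes that the unseen shells add nothing to the text of 17.4. It is a modest and inexpensive improvement worth making before unblinding.

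**What to change.** Add to SAP 17.4 a shift table of baseline interpretation category against the worst post-baseline category per subject, by dose level and pooled placebo within each study part. In the multiple-dose part, also show the shift to each post-dose visit. Keep the by-visit counts if wanted.

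State three conventions with it: baseline follows SAP 6.5; whether unscheduled and early termination ECGs count towards the worst category (SAP 6.6 keeps unscheduled values out of summary statistics but lets them contribute to the assessment of outliers); and how subjects without a baseline ECG are shown. If the shells already contain this table, the text of 17.4 should say so.

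The cost is one extra descriptive table, sparsely filled at these group sizes. It needs no new assessments, no new data and no change to the protocol.
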